4.2 Premedication to prevent infusion reaction

(1) Analysis sets to be used

Safety analysis set, safety analysis set (Hodgkin's lymphoma), and safety analysis set (anaplastic large-cell lymphoma)

(2) Data to be analyzed

For each cycle, patients will be stratified into the following categories, and the frequency will be calculated:

Data item	Category
Premedication to prevent infusion reaction	Absent, present, or unknown
Specific premedication(s) used to prevent infusion reaction	Acetaminophen, antihistamines, and/or corticosteroids
Specific premedication(s) used to prevent infusion reaction (in each patient)	Acetaminophen, antihistamines, corticosteroids, acetaminophen + antihistamines, acetaminophen + corticosteroids, antihistamines + corticosteroids, or acetaminophen + antihistamines + corticosteroids

(3) Figure/table number

Tables 4.2-1 to 4.2-3

4.3 Patient demographics and baseline characteristics by initial dose of Adcetris

(1) Analysis sets to be used

Patients included in safety evaluation and patients included in safety evaluation (Hodgkin's lymphoma) or patients included in safety evaluation (anaplastic large-cell lymphoma)

(2) Data to be analyzed

For each data item, patients will be stratified into the following categories, and the frequency will be calculated by initial dose of Adcetris (<1.2 mg/kg, 1.2 mg/kg, >1.2 mg/kg to <1.8 mg/kg, 1.8 mg/kg, or >1.8 mg/kg):

Data item	Category
Age	<18 years, 18 to 39 years, 40 to 64 years, 65 to 74 years, or ≥75 years
ECOG Performance Status	0, 1, 2, 3, or 4
Concurrent hepatic disorders	Absent or present
Grade of hepatic disorder (Grade based on AST)	None, Grade 1, Grade 2, ≥Grade 3, or unknown

Data item	Category
and ALT levels)	
Concurrent renal disorders	Absent or present
Grade of renal disorder (Grade based on serum creatinine)	None, Grade 1, Grade 2, \geq Grade 3, or unknown
Concurrent infection	Absent or present
Concurrent peripheral nerve disorder	None, Grade 1, Grade 2, Grade 3, Grade 4, or unknown

(3) Figure/table number

Tables 4.3-1 to 4.3-3

5.0 Safety Analysis

5.1 Occurrences of adverse events and adverse drug reactions/infections

5.1.1 Occurrence of adverse events

(1) Analysis sets to be used

Safety analysis set, safety analysis set (Hodgkin’s lymphoma), and safety analysis set (anaplastic large-cell lymphoma)

(2) Data to be analyzed

Data listed below will be analyzed.

For data entered in the field of “Adverse events: [1] Peripheral nerve disorders] in the case report form, MedDRA PT Code for peripheral sensory neuropathy, peripheral motor neuropathy, or peripheral neuropathy should be assigned, regardless of data entered in “Symptoms” field (see Section 1.2, the same applies hereinafter).

MedDRA PT Code for “Infusion related reaction” should be assigned to the field of “Adverse events: [4] Infusion reaction” in the case report form, regardless of data entered in “Symptoms” field (see Section 1.2, the same applies hereinafter).

Neutrophil count decreased (PT Code 10029366) will be replaced by Neutropenia (PT Code 10029354), Lymphocyte count decreased (PT Code 10025256) by Lymphopenia (PT Code 10025327), White blood cell count decreased (PT Code 10047942) by Leukopenia (PT Code 10024384), and Platelet count decreased (PT Code 10035528) by Thrombocytopenia (PT Code 10043554) (the same applies hereinafter).

Data item	Data to be analyzed
Number of patients with adverse events	Number of patients experiencing adverse events
Number of adverse events	Number of adverse events observed. If the same patient has multiple occurrences of the same adverse event (PT), the total number of occurrences will be calculated.
Percentage of patients with adverse events	Is calculated using the following formula: number of patients with adverse events/number of patients included in the safety analysis set × 100.
Type of adverse events	The incidence of adverse events will be calculated by SOC and PT. For SOC, the number and percentage of patients with adverse events will be calculated. For PT, the number and percentage of adverse events will be calculated. SOCs will be presented in the internationally agreed order, and PTs will be presented in ascending order of HLGT and PT codes if their SOCs are “Investigations,” and in ascending order of PT code otherwise. If the same patient has multiple occurrences of the same adverse event (PT), the event will be counted once per patient.

(3) Figure/table number

Tables 5.1-1 to 5.1.1-3

5.1.2 Occurrence of adverse drug reactions/infections

(1) Analysis sets to be used

Safety analysis set, safety analysis set (Hodgkin’s lymphoma), and safety analysis set (anaplastic large-cell lymphoma)

(2) Data to be analyzed

Data listed below will be analyzed.

Data item	Data to be analyzed
Number of patients with adverse drug reactions, etc.	Number of patients experiencing adverse drug reactions, etc.
Number of adverse drug reactions, etc.	Number of adverse drug reactions, etc., observed. If the same patient has multiple occurrences of the same adverse drug reaction, etc. (PT), the total number of occurrences will be calculated.
Percentage of patients with adverse drug reactions, etc.	Is calculated using the following formula: number of patients with adverse drug reactions, etc./number of patients included in the safety analysis set × 100.
Type of adverse drug reactions, etc.	The incidence of adverse drug reactions, etc., will be calculated by SOC and PT. For SOC, the number and percentage of patients with adverse drug reactions, etc., will be calculated. For PT, the number and percentage of adverse drug reactions, etc., will be calculated. SOCs will be presented in the internationally agreed order, and PTs will be presented in ascending order of HLTG and PT codes if their SOCs are “Investigations,” and in ascending order of PT code otherwise. If the same patient has multiple occurrences of the same adverse drug reaction, etc. (PT), the reaction will be counted once per patient.

(3) Figure/table number

Tables 5.1-2 to 5.1.2-3

5.2 Seriousness, CTCAE Grade (the worst one), time of onset, time to the worst grade, and occurrences of adverse events and adverse drug reactions/infections by outcome

5.2.1 Seriousness, CTCAE Grade (the worst one), time of onset, time to the worst grade, and occurrence of adverse events by outcome

(1) Analysis sets to be used

Safety analysis set, safety analysis set (Hodgkin’s lymphoma), and safety analysis set (anaplastic large-cell lymphoma)

(2) Data to be analyzed

For each data item, patients will be stratified into the following categories, and the type of adverse events will be analyzed:

Data item	Category
Seriousness	Serious or non-serious
CTCAE Grade (the worst one)	Grade 1, Grade 2, Grade 3, Grade 4, Grade 5, or unknown
Time of onset	1 to 7 days, 8 to 14 days, 15 to 21 days, 22 to 84 days, 85 to 168 days, 169 to 252 days, 253 to 336 days, ≥ 337 days, or unknown
	1 to 21 days, 22 to 42 days, 43 to 63 days, (segmented similarly using a 21-day time window thereafter), 316 to 336 days, ≥ 337 days, or unknown
Time to the worst grade	1 to 7 days, 8 to 14 days, 15 to 21 days, 22 to 84 days, 85 to 168 days, 169 to 252 days, 253 to 336 days, ≥ 337 days, or unknown
	1 to 21 days, 22 to 42 days, 43 to 63 days, (segmented similarly using a 21-day time window thereafter), 316 to 336 days, ≥ 337 days, or unknown
Outcome	Recovered/resolved, recovering/resolving, not recovered/not resolved, recovered/resolved with sequelae, died/fatal, unknown, or not provided

The type of adverse events will be analyzed as follows:

Data item	Data to be analyzed
Number of patients	Number of patients with adverse events by SOC/PT
Number of adverse events, etc.	Number of adverse events observed by SOC/PT If the same patient has multiple occurrences of the same adverse event (PT), all these occurrences will be counted (i.e., the overlap should be reflected).
Seriousness, CTCAE Grade (the worst one), time of onset, time to the worst grade, and outcome	The number of adverse events will be calculated by SOC and PT. SOCs will be presented in the internationally agreed order, and PTs will be presented in ascending order of HLGT and PT codes if their SOCs are “Investigations,” and in ascending order of PT code otherwise. If the same patient has multiple occurrences of the same adverse event (PT), the total number of occurrences will be calculated per category (for example, if the same patient has one episode of serious diarrhea and one episode of non-serious diarrhea, these events will be counted once for each category). If the same patient has multiple occurrences of the same adverse event classified into the same category, all these occurrences will be counted (i.e., the overlap should be reflected).

(3) Figure/table number

Tables 5.2.1-1 to 5.2.1-3

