### a) Peripheral nerve disorders

Peripheral nerve disorders are frequently observed after treatment with Adcetris. If the event of peripheral nerve disorder becomes severe, it is difficult to continue treatment with Adcetris. It is important to control the onset of the event to allow for continuation of treatment (including dose reduction and restart of treatment after treatment interruption). Therefore, the profile of peripheral nerve disorders in Japanese patients as an adverse event of particular interest will be determined (i.e., information useful for continuation of treatment with Adcetris, including risk factors, commonly reported time to onset, outcomes, and the status of treatment with Adcetris, will be collected).

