Serious adverse events	
Adverse events considered “serious” by the investigator.
 
Events listed in the MedDRA Coding List in the Takeda Medically Significant AE List should be regarded as serious even if they are considered “non-serious” by the investigator.

Number of patients with adverse events/adverse drug reactions	Number of patients experiencing adverse events or adverse drug reactions, etc.
Number of adverse events/adverse drug reactions	Number of adverse events or adverse drug reactions, etc., observed
Percentage of patients with adverse events/adverse drug reactions	
[For safety analysis using patients included in the safety analysis set]
 
Is calculated using the following formula: (number of patients with adverse events/adverse drug reactions) / (number of patients included in the safety analysis set) × 100.
 
[For safety analysis using patients excluded from the safety analysis set]
 
Is calculated using the following formula: (number of patients with adverse events/adverse drug reactions) / (number of patients excluded from the safety analysis set) × 100.

Percentage of adverse events/adverse drug reactions observed	
[For safety analysis using patients included in the safety analysis set]
 
Is calculated using the following formula: (number of adverse events/adverse drug reactions observed) / (number of patients included in the safety analysis set) × 100.
 
[For safety analysis using patients excluded from the safety analysis set]
 
Is calculated using the following formula:(number of adverse events/adverse drug reactions observed) / (number of patients excluded from the safety analysis set) × 100.

Time of onset	
Is calculated using the following formula: date of onset of adverse events (or adverse drug reactions, etc.) – date of the initial dose of Adcetris + 1.
 
If the day, month, and year of onset of adverse events (or adverse drug reactions, etc.) are unknown, the time of onset should be handled as missing, and the category for the time of onset should be “unknown.”

Time to the worst grade	Is calculated using the following formula: date of the worst CTCAE grade – date of the initial dose of Adcetris + 1.

Term	Definition																									
	If the day, month, and year of the worst CTCAE grade are unknown, the date of the worst CTCAE grade should be handled as missing, and the category for the date of the worst CTCAE grade should be “unknown.”																									

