4.0 Treatment Given

4.1 Treatment given

(1) Analysis sets to be used

Safety analysis set, safety analysis set (Hodgkin’s lymphoma), and safety analysis set (anaplastic large-cell lymphoma)

(2) Data to be analyzed

For each data item, patients will be stratified into the following categories below, and the frequency will be calculated. In addition, summary statistics of continuous variable will be calculated:

Data item	Category
Initial dose of Adcetris	<1.2 mg/kg, 1.2 mg/kg, >1.2 mg/kg to <1.8 mg/kg, 1.8 mg/kg, or >1.8 mg/kg
Mean dose of Adcetris	<1.2 mg/kg, 1.2 mg/kg, >1.2 mg/kg to <1.8 mg/kg, 1.8 mg/kg, or >1.8 mg/kg
Dose of Adcetris per 3 weeks	<1.2 mg/kg, 1.2 mg/kg, >1.2 mg/kg to <1.8 mg/kg, 1.8 mg/kg, or >1.8 mg/kg
Duration of treatment with Adcetris	1, 2, 3, 4, 5, 6, 7, 8, 9, 10, 11, 12, 13, 14, 15, 16, or ≥ 17 cycles
Reason(s) for discontinuation of Adcetris	Treatment goal achieved, adverse event(s), lost to follow-up, transfer to another hospital, pregnancy, inadequate response, and/or other
Post-baseline hematopoietic stem cell transplantation	Absent, present, or unknown
Type of post-baseline hematopoietic stem cell transplantation	Autologous or homologous
Days from the date of the last dose of Adcetris to hematopoietic stem cell transplantation (autologous) (Post-baseline hematopoietic stem cell transplantation: autologous)	-
Duration of treatment with Adcetris prior to	-

hematopoietic stem cell transplantation (autologous) (Post-baseline hematopoietic stem cell transplantation: autologous)	
Days from the date of the last dose of Adcetris to hematopoietic stem cell transplantation (homologous) (Post-baseline hematopoietic stem cell transplantation: homologous)	-
Duration of treatment with Adcetris prior to hematopoietic stem cell transplantation (homologous) (Post-baseline hematopoietic stem cell transplantation: homologous)	-
Drug(s) other than Adcetris used for the treatment of the primary disease	Absent or present
Drug(s) used for the prevention of infection	Absent or present
Specific drug(s) used for the prevention of infection	Antibiotics/synthetic antibacterial agents, antifungals, antivirals, trimethoprim-sulfamethoxazole combinations, and/or other prophylactics against infections

(3) Figure/table number

Tables 4.1-1 to 4.1-3

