	1 to 21 days, 22 to 42 days, 43 to 63 days, (segmented similarly using a 21-day time window thereafter), 316 to 336 days, ≥ 337 days, or unknown
Outcome	Recovered/resolved, recovering/resolving, not recovered/not resolved, recovered/resolved with sequelae, died/fatal, unknown, or not provided

The type of adverse drug reactions, etc., will be analyzed as follows:

Data item	Data to be analyzed
Number of patients	Number of patients with adverse drug reactions, etc., by SOC/PT If the same patient has multiple occurrences of the same adverse drug reactions, etc. (PT), all these occurrences will be counted (i.e., the overlap should be reflected).
Number of adverse drug reactions, etc.	Number of adverse drug reactions, etc., observed by SOC/PT
Seriousness, CTCAE Grade (the worst one), time of onset, time to the worst grade, and outcome	The number of adverse drug reactions, etc., will be calculated by SOC and PT. SOC’s will be presented in the internationally agreed order, and PT’s will be presented in ascending order of HLGTT and PT codes if their SOC’s are “Investigations,” and in ascending order of PT code otherwise. If the same patient has multiple occurrences of the same adverse drug reaction, etc. (PT), the total number of occurrences will be

	calculated per category (for example, if the same patient has one episode of serious diarrhea and one episode of non-serious diarrhea, these adverse drug reactions will be counted once for each category). If the same patient has multiple occurrences of the same adverse drug reaction, etc., classified into the same category, all these occurrences will be counted (i.e., the overlap should be reflected).
--	--

(3) Figure/table number

Tables 5.2.3-1 to 5.2.3-3

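### Time-of-onset tables give event counts per interval with no number at risk, so a change in risk over time cannot be separated from loss of exposure

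*SAP*

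**What the plan says.** Section numbers are those of the SAP printed first in the file.

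- **Intervals.** SAP 5.2.1 (adverse events) and 5.2.3 (adverse drug reactions) use two sets. One is unequal: "1 to 7 days, 8 to 14 days, 15 to 21 days, 22 to 84 days, 85 to 168 days", then two further 84-day intervals to day 336 and an open-ended one from day 337. The other uses equal windows: "segmented similarly using a 21-day time window thereafter), 316 to 336 days", again followed by an open-ended interval.
- **Statistic per interval.** For adverse events: "The number of adverse events will be calculated by SOC and PT". For adverse drug reactions: "The number of adverse drug reactions, etc., will be calculated by SOC and PT". Repeats of the same event within a category are not collapsed: "all these occurrences will be counted (i.e., the overlap should be reflected". Supplemental SAP 2.1 keeps event counts for time of onset.
- **Denominator.** None is attached to the intervals. The general event percentage in the SAP's definitions table is "number of adverse events/adverse drug reactions observed) / (number of patients included in the safety analysis set) × 100", which is fixed over time.
- **Observation.** Under protocol 9.2.5, adverse events are collected for 16 cycles, or up to discontinuation if that comes first.
- **Aim.** Protocol 10.4.1 calls for event frequency by time of onset. For peripheral nerve disorders, protocol 9.2.5 lists the information wanted to support continued treatment, "including risk factors, commonly reported time to onset, outcomes, and the status of treatment with Adcetris".
- **Exposure elsewhere.** SAP 4.1 reports patients by treatment duration: "1, 2, 3, 4, 5, 6, 7, 8, 9, 10, 11, 12, 13, 14, 15, 16, or ≥ 17 cycles".

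**The concern.** A count in an interval is the product of the event rate and the patient-time observed there. Patient-time falls as patients stop treatment, and in the unequal set it also changes because the intervals run from 7 to 84 days. Without the patient-time, a reader cannot tell a falling risk from a shrinking group, or a rising risk from a wider interval.

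This matters most for peripheral nerve disorders, where time to onset is a named aim. SAP 5.9.1 to 5.9.4 cover grade, background factors, action taken and outcome for these disorders, but not timing, so the count tables are the only planned summary of it. The protocol also notes that severe nerve disorder makes it hard to continue treatment, so the event itself can remove patients from later intervals. A prescriber who takes low late counts to mean low late risk could be misled.

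**Working it through.** **The plan's own figure.** The only design figure is the enrolment of 140 (protocol 3.2), set to see at least 10 patients with infusion reaction at 11% with 95% probability. The exact binomial probability is 0.949 at n = 139 and 0.952 at n = 140, so the figure reproduces. It is not in dispute and serves below only as the starting number.

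**Inputs.**
- N = 140 (protocol 3.1).
- Cycle length 21 days and 16 cycles (protocol 7.1), so 16 × 21 = 336 days.
- Interval limits from SAP 5.2.1.
- Assumed: a constant 0.10 events per patient per 21 days.
- Assumed: exponential discontinuation with a median of m cycles. The documents give no rate, so m is taken as 4, 8, 12 and 16.

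**Formulas.** With h = ln 2 / (21m), patient-time between days a and b is PT(a,b) = N(e^(−ha) − e^(−hb))/h. The expected count is 0.10 × PT/21. The ratio of the last 21-day window (days 316–336) to the first is e^(−315h) = 2^(−15/m), which depends on neither N nor the event rate.

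**One case in full, m = 8.** h = 0.6931/168 = 0.004126 per day. PT(0,21) = 2,816 patient-days, giving 13.4 events. PT(315,336) = 768 patient-days, giving 3.7 events. The ratio is 2^(−1.875) = 0.27. Dividing each count by its own patient-time returns 0.10 per 21 days in both windows.

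**21-day windows, constant true rate.**

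| Median cycles | Events, days 1–21 | Events, days 316–336 | Ratio | On treatment at day 316 | Rise in true rate needed to keep counts level |
|---|---|---|---|---|---|
| 4 | 12.9 | 1.0 | 7% | 10 | 13.5-fold |
| 8 | 13.4 | 3.7 | 27% | 38 | 3.7-fold |
| 12 | 13.6 | 5.7 | 42% | 59 | 2.4-fold |
| 16 | 13.7 | 7.2 | 52% | 73 | 1.9-fold |
| No discontinuation | 14.0 | 14.0 | 100% | 140 | none |

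**The reverse case.** With no discontinuation and a true rate that halves every 4 cycles, the counts run from 14.0 to 14.0 × 2^(−15/4) = 1.0. The ratio is the same 7% as in the first row. The planned table cannot tell these two situations apart.

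**Unequal intervals, constant true rate.**

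| Median cycles | Events, days 1–7 | Events, days 253–336 |
|---|---|---|
| 4 | 4.5 | 5.0 |
| 8 | 4.6 | 16.7 |
| 12 | 4.6 | 25.0 |
| 16 | 4.6 | 30.6 |
| No discontinuation | 4.7 | 56.0 |

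Here the later interval holds more events at every median, because it is twelve times as wide.

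**The case against.** The strongest reply has four parts.

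- **The denominators already exist.** SAP 4.1 gives patients by number of cycles, 4.2 gives premedication status cycle by cycle, and 5.8.1 gives laboratory summaries per cycle with the number of patients. The 21-day windows match the nominal cycle. This is right as far as it goes: what is missing is a denominator in the onset tables, not all exposure data in the plan. But no section links the two. The onset tables run on days since first dose, and the SAP itself lists treatment delay as an action, so cycles and days drift apart.
- **The tables only describe.** Protocol 10.4.1 asks for frequency by time of onset, not a hazard, and no test or sample size rests on these tables. That limits the seriousness. It does not make a count informative about timing when exposure is unknown.
- **Some events are covered elsewhere.** SAP 5.9.11 and 5.9.12 give infusion reactions an onset analysis relative to the infusion and a per-dose denominator. This stands. SAP 5.10 and 5.11 list dose and onset dates by patient for peripheral nerve disorders and neutropenia, but a listing is not a summary.
- **Observation does not always stop at discontinuation.** Protocol 7.4 keeps patients who stop for an adverse event under observation, where possible, until it resolves or improves. This is a partial exception and does not cover patients who stop for other reasons.

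A reader might go further and infer that late intervals will look safer only because patients have stopped treatment. The documents do not support that. They contain no discontinuation rate and no event data, a genuine fall in risk would produce the same counts, and in the unequal set later intervals can look worse.

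**Conclusion.** The gap is real and moderate. As planned, the time-of-onset tables cannot separate a change in risk from loss of exposure or, in the unequal set, from interval width. In the 21-day set, attrition alone would reduce the last window to about 7% to 52% of the first under a constant rate. That range rests on exponential discontinuation with an assumed median of 4 to 16 cycles and would change with the true pattern. The direction for the 21-day set does not depend on the exact rate: any discontinuation lowers late counts relative to early ones at constant risk. No single direction can be stated for the unequal set. Nothing confirmatory depends on these tables, but a stated safety aim of the surveillance does.

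**What to change.** In the 21-day tables of SAP 5.2.1, 5.2.3 and Supplemental SAP 2.1, add for each interval the number of patients under observation at its start, the patient-time, and events per patient-time. Do the same for the unequal-width set, or state that it is not to be used for comparing risk over time. The open-ended interval from day 337 needs patient-time in particular, since it has no width.

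Add a cumulative incidence curve of first onset, with numbers at risk beneath it, for at least peripheral nerve disorders, infections, neutropenia and pulmonary disorders. Infusion reactions can rely on SAP 5.9.11 and 5.9.12. State which date ends observation, and how discontinuation and death are handled.

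The inputs are dosing dates, onset dates and the date of final observation, all already on the case report form. The cost is a few extra rows per table and about four figures. No new data collection and no change to the sample size are needed.
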